Aim #1- (a) Cardiovascular Risk Trajectories (H1): There is no validated CV risk engine developed with a prediabetes population. Therefore, we propose to use the ACC/AHA 10-year pooled CV risk engine to estimate annual rate of change in CV risk as our primary outcome. We will use the lipid equation for patients with lipid data available to calculate CV risk at the index and all post-index visits and, to minimize missing CV risk values, the BMI equation at the index and all post-index visits for the remaining patients. The BMI equation estimates higher CV risk relative to the lipid equation. Because the calculation method will be consistent across all visits within each patient this difference will not bias the estimated rate of change in CV risk. CV risk scores for each patient will be calculated at each primary care visit from the index through the entire follow-up period using available EHR data elements. As depicted in Figure 2 Step A, at each visit we will search for the most recent data elements, looking back over a period appropriate for each risk component (i.e., 12 months for BP values or medications, DM diagnosis, smoking, BMI; 48 months for lipids). H1 will be supported if the annual rate of change in CV risk scores from the index visit through the end of the follow-up period is lower (ie, less increase) among patients in the CDS relative to UC clinics; (b) Modifiable diabetes and CV risk factors (H2): Risk factors needed to calculate the CV risk scores (weight, systolic blood pressure, HDL-c, LDL-c, totalcholesterol, smoking), are extracted from EHR files as in Figure 2 Step A. H2 will be supported if annual rate of change in CV risk component trajectories are lower among patients in the CDS relative to UC clinics; (c) Metformin and statin use (H3): Data to assess drug treatment are from EHR files such as prescribed medications. The presence or absence of appropriate drug use will be assessed at each visit. H3 will be supported if appropriate drug use improves over the follow-up period among patients in the CDS clinics relative to UC patients.

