Measures of Covariates for Primary and Secondary Analyses: One predictor of CV risk, risk factor, and drug use outcomes is the binary indicator for study condition (CDS or UC). The second key predictor is time elapsed in years between the patient's index visit to each subsequent measurement. Several other measures merit consideration as dependent outcomes, moderators or mediators in primary analyses. These include (a) number of PCP patient encounters, (b) patient characteristics including demographics and pre-intervention clinical values and comorbidities (EHR ICD-10 diagnosis codes and problem lists), and (c) provider characteristics such as age, gender, type of provider, full-time or part-time work status,, specialty board certification status, and proportion of eligible study patients. Patient or provider characteristics may also be used to adjust for covariate imbalance introduced by clinic randomization.

Analysis Plan.

Aim 1 Analytic Approach. Aim 1 pertains to the effectiveness of the Prediabetes CDS intervention, predicting that it will improve the annual rate of change in CV risk (CVR) and individual risk factors relative to UC. Patients age 40-75 at index are included in the Aim 1 analyses because the CDS was programmed to deliver the intervention via treatment recommendations (Figure 2, Step B) to this age group. Rate of change outcomes (e.g., H1, H2) will be tested using random coefficients models in which all available index and post-index outcomes (H1 CV risk, H2 CV risk factors) will be predictedfrom fixed effects for clinic-randomized treatment group, years elapsed since index CVR, the treatment by years elapsed interaction and the index outcome value. Outcomes measured only once per person will follow the same approach, omitting predictors that incorporate years elapsed since index and where warranted including an offset for follow-up time.

Random clinic and patient intercepts will account for clustered observations as appropriate. The link function and error distribution for each model will be determined by the distribution of each outcome. The relationships between years elapsed and CV risk and risk factor outcomes are expected to be linear. The tenability of this assumption will be checked for each outcome and more complex relationships (e.g., non-linear, spline) modeled if warranted.

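### The H1 model crosses no baseline covariate with time, so chance age differences between clinics may cost precision in the treatment-by-years estimate

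*Combined protocol and SAP*

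**What the plan says.** **Outcome.** Under Definition and Measurement of Variables, Aim #1, the investigators "propose to use the ACC/AHA 10-year pooled CV risk engine to estimate annual rate of change in CV risk as our primary outcome". H1 is supported if the annual change from the index visit "through the end of the follow-up period is lower (ie, less increase) among patients in the CDS relative to UC clinics".

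**Model.** The Aim 1 Analytic Approach lists four fixed effects: treatment group, years elapsed, "the treatment by years elapsed interaction and the index outcome value". On clustering it says: "Random clinic and patient intercepts will account for clustered observations as appropriate". The text that follows makes treatment-by-years the estimate of the CDS effect on annual change. The link and error distribution are left to depend on each outcome's distribution.

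**Population.** "Patients age 40-75 at index are included in the Aim 1 analyses".

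**Other covariates.** Measures of Covariates for Primary and Secondary Analyses says: "Patient or provider characteristics may also be used to adjust for covariate imbalance introduced by clinic randomization". The same section says: "Several other measures merit consideration as dependent outcomes, moderators or mediators in primary analyses", and its list includes demographics and pre-intervention clinical values. It names no covariate for H1, no trigger for adjustment and no product with years.

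**Randomisation.** The design overview blocks the 34 clinics on size and geographic service area. Patient age and CV risk are not blocking factors.

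**The concern.** H1 is a comparison of slopes, but the only baseline covariate specified for it adjusts levels. If patients of different ages have different slopes, a chance difference in mean age between the arms carries over into treatment-by-years. With 34 randomised units, and clinics ranging from 1 to 56 PCPs, such differences will not average out as well as they would with thousands of individually randomised patients. At stake is the precision of the primary estimate, and therefore power. Age at index is already held for every patient. The optional adjustment wording also leaves the form of the primary test to a choice made after imbalance has been seen.

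**Working it through.** **1. The plan's own power figures.** Section 2.2.6.1 uses Neff = N/[1 + (n - 1)ρ], three scores per patient and a patient ICC of 0.80. With 2,625 patients in 15 clinics (n = 175) and ρ = 0.001: Neff = 2625/1.174 = 2,236; effective scores = 3 x 2236/2.6 = 2,580; β = 2.80/√2580 = 0.055, as stated. Four of the six stated endpoints reproduce this way. At 11 providers per clinic I get 0.0458 against 0.044 and 0.0625 against 0.061, a separate and small matter. The calculation has no term for slopes that differ by age.

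**2. Why a main effect does not help.** For patient i, write the score as α + τT + βt + δTt + γx + clinic intercept + patient intercept + error, with x fixed at index. Between two visits the change is (β + δT)(t2 - t1) + error. γx cancels, whether x is the index score or age. If the true slope also contains θ x age, the unadjusted slope contrast estimates δ + θD, where D is the difference in mean age between arms. Under randomisation D averages zero, so θD adds variance and no systematic shift.

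**3. Size of D.** Assumed: age SD 8.5 years, 17 clinics per arm (no allocation ratio is stated), 6600/34 = 194 patients per clinic. SD(D) = √{2 x 8.5² x [1 + 193 x ICC]/(17 x 194)}.

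| Clinic ICC of age (assumed) | SD(D), years |
|---|---|
| 0.001 | 0.23 |
| 0.02 | 0.46 |
| 0.05 | 0.68 |

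Simulated values, with age clipped to 40-75, were 0.42-0.44 at ICC 0.02 and 0.63-0.71 at 0.05.

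**4. Simulated effect of adding age-by-years (identity scale).** All sets have 34 clinics. Growth rates, ICCs of age and noise levels are assumptions.

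| Set | Main assumptions | Reduction in variance of treatment-by-years |
|---|---|---|
| A | 3 visits/yr, patient ICC 0.80, growth 6% and 8%, 120 trials per setting | ICC 0.005: 9-21%; 0.02: 11-27%; 0.05: 30-47% |
| B | 4 scores over 26-38 months, growth 8%, residual slope SD 1 point/yr, extra clinic slope SD 0-0.2, 500 trials | ICC 0.02: 15-31%; 0.05: 35-52% |
| C | 9 scores, patient ICC 0.80, growth 6-8%, equal clinics, 400 trials | ICC 0.005: 8-17%; 0.02: 21-27%; 0.05: 30-53% |
| C, unequal clinics | as C, 1-56 PCPs | 2-20%; 25-40%; 40-53% |
| D | growth 6-8%, ICC 0.001-0.05, 400 trials | 3-47%; 3-9% at ICC 0.001 |
| E | growth 5-7%, ICC 0.001-0.05 | about 1-44%, never an increase |

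Example from A (ICC 0.02, 8%): the SD falls from 0.0797 to 0.0679, and 1 - (0.0679/0.0797)² = 27%. Example from B (ICC 0.02, 8%, no extra clinic slope variance): 0.077 to 0.064, or 31%. In that run the estimate's correlation with D was 0.56, and 0.56² = 0.31, so the gain is the share of variance that D explains.

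Over all of B's settings, with growth of 5-10%, age-by-years lowered variance by 0-66%, and the mean estimate stayed between -0.007 and 0.008 points/yr.

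**5. Where the gain vanishes.** If the slope does not depend on age or risk, it is zero. On a log scale, constant relative growth gives every patient the same slope, and set D then showed -0.6% to +0.2%.

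**6. Alternative product.** Index risk x years gave a variance ratio of 0.77-1.24 in A (it can make matters worse), a 2-34% reduction in C and a 1-71% reduction in B. Its value depends on how noisy the index score is assumed to be. No gain was shown for sex x years.

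**The case against.** **The premise is not in the documents.** This stands. They anticipate that the score may rise, but do not attribute this to age or say that it rises faster in older patients. Aim 1 also allows for a fall in the CDS arm, and the power analysis takes a zero slope in usual care. The point is therefore conditional.

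**The link function is open.** This also stands. A log scale could remove the problem. The plan does not commit to one.

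**The plan already permits adjustment.** This stands in part. A reader might infer that the index value is the only covariate allowed, or that any imbalance adjustment must be a main effect. The text says neither, and the moderator wording could cover an age-by-years term. But nothing commits the primary model to one. By contrast, the Aim 2 cost model does commit to demographics and baseline clinical risk factors.

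**The larger gains need a high ICC.** This stands. The plan's clinic ICCs are 0.001-0.02, and they are for the score, not age. The gains above 40% come from an age ICC of 0.05. With 120 trials, the approximate Monte Carlo interval for set A at 6% growth is -2% to 18% (ICC 0.005) and 0% to 22% (ICC 0.02).

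**A result is already known.** The note after Specific Aim 3 says that cost-effectiveness was dropped for lack of efficacy. Replacing the primary model now would be post hoc. This stands and shapes the fix.

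**Conclusion.** The point holds as a conditional loss of precision. No specified baseline covariate in the H1 model is crossed with years, and the optional adjustment is not tied to the slope. On the identity scale, with assumed growth of 5-8% per year of age and an age ICC of 0.001-0.05, age-by-years would lower the variance of treatment-by-years by roughly 0-50%. At an ICC of 0.02 or below the range is about 1-30%, although the unequal-clinic run at 0.02 reached 40%.

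Two stronger readings are not supported:

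- **Biased CDS effect.** A reader might infer this because an age difference in the realised trial would shift its estimate. Clinics are randomised, so the shift averages zero.
- **Inflated false-positive rate.** A patient-level test that ignored slope clustering rejected a true null in 4-21% of trials in set B (no extra clinic slope variance) and 8-25% in set C. That test is a proxy, not a fit of the planned model. The plan calls its models random coefficients models while naming only intercepts, so the documents do not settle whether slopes vary by clinic and patient.

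**What to change.** In the H1 model, add index age and index age x years as fixed effects whatever imbalance is observed, and let this replace the discretionary imbalance adjustment for the primary test. State the scale on which H1 is analysed, since the gain depends on it. Index risk x years may be considered, but the simulations do not agree well enough to require it, and there is no basis here for adding sex x years. Age-by-years does not replace random clinic and patient slopes, whose inclusion should be stated separately.

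If the primary analysis has been run, keep the planned model as primary and report the age-adjusted model beside it as a clearly labelled sensitivity analysis. A supportive analysis may re-score every visit with age held at its index value, so that the slope reflects changes in the other risk components.

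The cost is two fixed effects from data already held, plus a short change of wording. The risk is that a later change of model looks result-driven, which the labelling addresses.

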Official Title: Reducing CV Risk in Prediabetes Patients Using EHR-Based Decision Support

NCT Number: NCT02759055

Document Date: March 5, 2021

PROTOCOL

To improve implementation of evidence-based prediabetes care, a randomized study of the implementation and impact of a prediabetes Clinical Decision Support (CDS) intervention on cardiovascular (CV) risk in prediabetes patients (18-75 years old, body mass index (BMI) ≥25 kg/m², current smoker, uncontrolled blood pressure [BP] or lipids) is justified based on these considerations: (a) over 75% of rural primary care providers (PCP) now use EHR systems²²; (b) in a previous randomized trial, we showed that CDS in primary care clinics significantly improved BP and glucose control in adults with diabetes; (c) this CDS system elicits evidence-informed patient treatment preferences using human-computer interfaces; (d) the CDS system is minimally disruptive of clinic workflow with 80% use rates in targeted diabetes patients and 95% provider satisfaction; and (e) treatment and prioritization algorithms are Web- based and therefore easily updated and highly scalable to any medical group that uses EHRs.

The objective of this project is to systematically and pragmatically improve care and CV risk factors in a population of predominantly rural adult prediabetes patients at high risk for developing diabetes and CV events by implementing aWeb-based CDS system that integrates with local EMR systems and presents the patient and PCP with personalized, evidence-based drug and lifestyle treatment recommendations. To accomplish this objective, we addressed the following specific aims and hypotheses:

Specific Aim 1: Cluster-randomize 34 primary care clinics with 450 PCPs and over 11,000 high-risk adult prediabetes patients to one of two study arms: (a) Usual care (UC) clinics or (b) Intervention (CDS) clinics, which use an EHR-linked, Web-based Prediabetes CDS system designed to improve prediabetes care.

Hypothesis 1 (H1): Relative to those treated at UC clinics, eligible 18 to 75-year-old prediabetes patients at high CV risk treated at CDS clinics will have significantly more favorable trajectories in CV risk estimates over a median 24-month follow up.

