of hypertension with index visit BP ≥140/90 mm Hg or no diagnosis of hypertension but two consecutive BP ≥140/90 mm Hg, or ACC/AHA 10-year CV risk ≥7.5% and LDL either untested or ≥70 mg/dL and not on a statin, (g) no hospice care or chemotherapy for cancer within previous 12 months, and (h) have at least one subsequent primary care visit after the index visit. The patient accrual period (for first index visits) will be 12 months, followed by a 26-month observation period. Thus, patients will have 26 to 38 monthsof follow up, with an expected median of 32 months follow up after the index visit. Pilot data indicate that non- pregnant eligible adults have a median of 6 primary care visits over a 24-month period, ensuring broad inclusion in the analysis. We conservatively estimate an average of 25 eligible patients per consented study PCP with few losses due to death (<1%) in the study period. Few patients switch primary care clinics in Essentia and we accurately match over 98% of patients to a regular PCP. Ultimately, after accounting for all eligibility criteria, we anticipate over 6,600 eligible patients for Aim 1 and Aim 2 analyses. For Aim 1 and Aim 2 analyses we will retrospectively collect CV clinical information and will ask for a waiver of patient consent. The IRB has waived consent in prior and existing evidence-based CDS studies. Patients specifically recruited for focus groups and surveys will be consented and receive

modest compensation for those activities.

Description of Usual Care (UC) and PrediabetesCDS Intervention Conditions.

[figure not shown]
UC Condition. UC clinics and their consented PCPs will have no access to the CDS intervention.

Prediabetes CDS System: The Prediabetes CDS intervention is rooted in a series of antecedent studies that have developed successful forms of CDS for diabetes. The process flow of the intervention is shown in Figure 2.Specific steps in implementation of the Prediabetes CDS intervention are described below.

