The years elapsed parameter will estimate the annual rate of change in CV risk and risk factors among patients in UC clinics in the absence of intervention, while the treatment by years elapsed parameter estimates the difference in the annual rate of change among patients in the CDS relative to UC clinics. It is expected that CV risk will decrease, or increase at a slower rate, among patients in CDS relative to UC clinics. Similar patterns of improvement, or slower worsening, are expected for CV risk factors. Finally, the treatment group parameter is expected to estimate more appropriate pharmacologic use among patients in CDS compared to UC clinics.

2.2.6.1 H1 Sample size justification. We conducted a power analysis to estimate theminimum detectable slope of the treatment by time parameter (power=.80, α_2 =.05) given the anticipated sample size (15 CDS clinics, 7-11 providers per clinic * 25 patients per provider = 2625-4125 CDS patients, 3 CVR per patient).. The patient sample size was divided by the design effect, Neff = N / [1 + (n_{clus} – 1) ρ], to approximate the effective independent patient sample size (Neff) implied by clinic intraclass correlations (ICC) of ρ = .001-.02. The CVR sample sizes (Neff patient * 3 CVR/pt) were divided by the design effect implied by a patient ICC=0.80. The resulting effective CVR sample sizes were used to estimate the minimum detectable standardized linear regression coefficient (β_{CDS}) relative to β_{UC} =0. When ICC_{clin}=0.001, the minimum detectable β_{CDS} =0.044-0.055; when ICC_{clin}=0.005 β_{CDS} =0.061-0.070; and when ICC_{clin}=0.02 β_{CDS} =0.103-0.108.

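### The H1/H2 slope test lists only random intercepts, so the stated model carries no clinic-level variation in slopes in a clinic-randomized trial

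*Combined protocol and SAP*

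**What the plan says.** Specific Aim 1 sets the unit of randomization: "Cluster-randomize 34 primary care clinics". The Aim 1 Analytic Approach says that the rate-of-change outcomes for H1 and H2 "will be tested using random coefficients models in which all available index and post-index outcomes" are predicted from treatment group, years elapsed, their interaction and the index value. The tested quantity is the interaction: "the treatment by years elapsed parameter estimates the difference in the annual rate of change among patients in the CDS relative to UC clinics".

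The sentence on random terms is "Random clinic and patient intercepts will account for clustered observations as appropriate". It follows a sentence on a different kind of outcome: "Outcomes measured only once per person will follow the same approach", leaving out the time terms.

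For Aim 1 the document states no random slope for years elapsed at either level, no clinic-by-time variance, no cluster-robust variance and no clinic-based degrees of freedom. Estimation that allows for clustering by clinic with generalized estimating equations appears only under Aim 2, for costs. Section 2.2.6.1 (H1 sample size justification) does inflate for clinic ICCs of 0.001 to 0.02 when it derives the detectable treatment-by-time slope.

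**The concern.** In a clinic-randomized trial, the error term for the treatment effect has to include variation between clinics in the quantity being compared. Here that quantity is a slope. A clinic intercept describes how clinics differ in level, not how their trajectories differ. If the model is fitted with the listed terms only, patients within a clinic count as independent evidence about the slope, and so do repeated visits within a patient, once intercepts are removed. If slopes vary at either level, the standard errors for H1 and H2 are then too small.

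The protocol reports lack of efficacy when it explains why the cost-effectiveness hypothesis was dropped, so a false-positive H1 claim is not the main risk. A null result is read through its interval, and an interval that is too narrow overstates how much benefit or harm has been excluded. H2 also involves several separate slope tests, each open to the same error.

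**Working it through.** **1. The plan's own power figures.** Inputs from section 2.2.6.1: 15 CDS clinics, 175 to 275 patients per clinic (7 to 11 providers × 25), 3 risk values per patient, patient ICC 0.80, power 0.80, alpha 0.05 (read as two-sided).

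- Clinic design effect = 1 + (m − 1)ρ: from 1 + 174 × 0.001 = 1.174 to 1 + 274 × 0.02 = 6.48.
- Effective number of values = 3 × [15m / design effect] / (1 + 2 × 0.80); detectable slope = (1.960 + 0.842) / √(that number).
- ICC 0.001: 0.046–0.055 (plan 0.044–0.055). ICC 0.005: 0.063–0.070 (plan 0.061–0.070). ICC 0.02: 0.103–0.108 (plan the same).
- The two lower ends that differ match the plan if 300 patients per clinic are used instead of 275 (0.0443 and 0.0614). This does not affect the present point.
- With no clinic design effect: 0.041–0.051.

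The planning therefore lets clinic clustering roughly double the detectable slope at ICC 0.02.

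**2. What clinic intercepts do to the slope test.** With balanced visits, a patient's slope is Σ(t − t̄)y / Sxx, where Sxx = Σ(t − t̄)². A constant added to all visits contributes Σ(t − t̄) = 0. A generalized least squares check (34 clinics, 20 patients each, between-patient variance 0.80, residual 0.20) agrees:

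- The SE of treatment-by-years is 0.01819 with 3 visits and 0.01537 with 6 balanced visits, unchanged for clinic ICCs from 0 to 0.10. With 6 irregular visits it moves only from 0.01730 to 0.01729.
- A clinic slope variance does move it. With 60 patients per clinic and 6 visits it is 0.00888 at variance 0, 0.00952 at 0.0001 and 0.01148 at 0.00045.

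**3. Size under stated assumptions.**

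- From the documents: 6,600/34 ≈ 194 patients per clinic (taken as equal); 32 months of follow-up (Study Participants); 3 visits (power section) or 6 (median in the pilot data); residual variance 1 − 0.80 = 0.20.
- Assumed: slope SD 0.05, 0.10 or 0.15 outcome SD per year; clinic share s of slope variance 0.001 to 0.02. That range is borrowed from the plan's outcome ICC and is not a documented slope ICC.

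Per-patient variances with J equally spaced visits:

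- True: 0.20/Sxx + (1 − s)SD² + 194·s·SD²
- Reported, intercepts only: 0.20/Sxx + SD²/(J − 1)
- Reported, patient slopes added: 0.20/Sxx + SD²
- Rejection rate at nominal 5% = 2[1 − Φ(1.96/√(true/reported))]

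Over 2.667 years, Sxx = 3.556 (J = 3) or 4.978 (J = 6). Example with J = 6, SD 0.15, s = 0.02: true 0.0402 + 0.0221 + 0.0873 = 0.1495; reported 0.0402 + 0.0045 = 0.0447. The ratio is 3.35, the SE ratio 1.83 and the rejection rate 28.4%.

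| Slope SD | Intercepts only | Patient slopes fitted, clinic slopes omitted |
|---|---|---|
| 0.05 | 5.3–8.4% | 5.1–7.7% |
| 0.10 | 6.3–17.7% | 5.3–14.1% |
| 0.15 | 7.7–28.4% | 5.6–20.4% |

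The true SE is 1.02–1.83 times the reported SE with intercepts only, and 1.00–1.55 times with patient slopes. At share 0.001 alone, rejection is 5.3–11.0% and 5.1–5.8%. With 24 months instead of 32, since H1 is stated "over a median 24-month follow up", the full ranges are 5.2–20.4% and 5.1–15.8%.

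**4. Simulation** (4,000 replicates per setting), slope SD 0.15, 6 visits:

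| Clinic share | Intercepts only | Patient slopes only | Clinic-mean-slope t-test, 32 df |
|---|---|---|---|
| 0.001 | 10.8% | 6.0% | 5.3% |
| 0.02 | 27.5% | 19.6% | 4.7% |

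The clinic-mean-slope test rejected 4.5–5.3% in all 12 settings run. With zero slope variance, the intercepts-only test rejected 4.6% (3 visits) and 5.8% (6 visits), close to nominal.

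**5. Interval width.** t(0.975, 32)/1.96 = 2.037/1.96 = 1.039. Multiplied by the SE ratios, a valid 95% interval is 1.05–1.90 times as wide as the intercepts-only interval, or 1.04–1.61 times as wide if patient slopes are fitted.

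**The case against.** The strongest reply is that the label random coefficients models normally means that the time slope varies randomly. The intercept sentence comes straight after the text on outcomes measured once, where intercepts are all that can be fitted. It is qualified by as appropriate, and it does not say that intercepts are the only random terms. On that reading patient slopes are modelled and the effect is small over most of the assumed range: 5.1–5.8% at share 0.001, and 5.5–9.1% at share 0.005. Rates above 10% then need share 0.02 with slope SD of at least 0.10.

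This is a fair reason not to lean on the 28.4% figure, which needs the less favourable reading together with the largest SD, the largest share and six visits. It does not settle the point. The label does not say at which level slopes vary, and patient slopes alone still leave out variation at the level of randomization.

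It is also true that the slope SD and clinic share are not in the documents, and that a design effect in planning is conservative in itself. The power section suggests that the authors meant clinic clustering to count for this parameter. That supports writing the term into the model, because the listed terms do not supply it.

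Finally, unweighted clinic means lose efficiency when clinics differ in size, and the protocol gives a range of 1 to 56 PCPs per clinic. That stands, but it bears on only one of the alternative remedies.

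**Conclusion.** The concern holds. The stated random terms do not carry clinic-level slope variation into the H1/H2 test, and neither the model label nor the as-appropriate qualifier supplies it. That conclusion rests on the text and on the cancellation in step 2, not on any assumed variance.

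The size does rest on assumptions. Inflation is nil if slopes do not vary, slight at the low end of the grid, and substantial only if clinics differ appreciably in their trajectories. The calculation also assumes equal clinics and takes the whole anticipated sample ("we anticipate over 6,600 eligible patients for Aim 1 and Aim 2 analyses"), although Aim 1 is restricted to ages 40–75. Fewer patients per clinic would reduce the inflation from clinic slopes; unequal clinic sizes would increase it. The point should be fixed, chiefly for the width of the H1 interval and for the individual H2 tests. Confidence is medium, because the model actually intended may already include slopes.

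**What to change.** For H1 and H2, state random intercepts and random years-elapsed slopes at both patient and clinic level, and test treatment-by-years with clinic-based degrees of freedom (about 34 − 2 = 32). A cluster-robust variance by clinic with a small-sample correction would also do, as would an analysis of clinic mean slopes with a stated weighting for unequal clinic sizes. Say in advance what will be done if the clinic slope variance is estimated at zero.

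If an intercept-only model has already been fitted, re-run it and report the corrected intervals. If clinic slopes were fitted, one clarifying sentence closes the point.

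The cost is plan wording, model code and possibly a modest re-analysis. Intervals will be somewhat wider; about 4% of that comes from the degrees of freedom alone.
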